## 1 PROTOCOL REVISION HISTORY

Date/Name	Description
03 Aug 2017 by 	Final Protocol

## 5 SYNOPSIS

Compound:	MK-3866
Clinical Indication:	Treatment of gram-negative bacterial infections
Study Phase and Type:	Phase 1 - Interventional
Study Objectives and Estimations:	
Primary:
 
Objective 1: To compare the plasma pharmacokinetics (e.g., AUC0-∞, AUC0-last, AUC0-24, Ceoi (Cmax), Tmax, elimination terminal t1/2, CL, and Vz) of MK-3866 following a single intravenous (IV) dose in subjects with mild renal impairment (RI) to those of mean healthy matched control subjects.
 
Estimation 1: The AUC0-∞ following a single IV dose of MK-3866 administered to subjects with mild RI will be estimated and compared to the AUC0-∞ when administered to mean healthy matched control subjects.
 
Objective 2: To compare the plasma pharmacokinetics (e.g., AUC0-∞, AUC0-last, AUC0-24, Ceoi (Cmax), Tmax, elimination terminal t1/2, CL, and Vz) of MK-3866 following a single IV dose in subjects with moderate RI to those of mean healthy matched control subjects.
 
Estimation 2: The AUC0-∞ following a single IV dose of MK-3866 administered to subjects with moderate RI will be estimated and compared to the AUC0-∞ when administered to mean healthy matched control subjects.
 
Objective 3: To compare the plasma pharmacokinetics (e.g., AUC0-∞, AUC0-last, AUC0-24, Ceoi (Cmax), Tmax, elimination terminal t1/2, CL, and Vz) of MK-3866 following a single IV dose in subjects with severe RI to those of healthy matched control subjects.
 
Estimation 3: The AUC0-∞ following a single IV dose of MK-3866 administered to subjects with severe RI will be estimated and compared to the AUC0-∞ when administered to mean healthy matched control subjects.
 
Objective 4: To compare the plasma pharmacokinetics (e.g., AUC0-∞, AUC0-last, AUC0-24, Ceoi (Cmax), Tmax, elimination terminal t1/2, CL, and Vz) of MK-3866 following a single IV dose administered after hemodialysis (HD) in subjects

	
with end stage renal disease (ESRD) undergoing HD to those of mean healthy matched control subjects.
 
Estimation 4: The AUC0-∞ following a single IV dose of MK-3866 administered after HD to subjects with ESRD will be estimated and compared to the AUC0-∞ when administered to mean healthy matched control subjects.
 
Objective 5: To compare the plasma pharmacokinetics (e.g., AUC0-∞, AUC0-last, AUC0-24, Ceoi (Cmax), Tmax, elimination terminal t1/2, CL, and Vd) of MK-3866 following a single IV dose administered prior to HD in subjects with ESRD to those of mean healthy matched control subjects.
 
Estimation 5: The AUC0-∞ following a single IV dose of MK-3866 administered prior to HD to subjects with ESRD will be estimated and compared to the AUC0-∞ when administered to mean healthy matched control subjects.
 
Secondary:
 
Objective 1: To investigate the extent to which MK-3866 is removed by HD.
 
Estimation 1: The extent to which MK-3866 is removed by HD from the plasma (e.g., Ca, Cv, AUCD, AUC[1-4.5]Ca, AUC[1-4.5]Cv, and CLD,plasma) or the dialysate (e.g., CD, AD, rr, AD,total, and CLD,dialysate) will be estimated.
 
Objective 2: To compare the urine pharmacokinetics (e.g., Ae0-24, Fe, and CLr) of MK-3866 following a single IV dose of MK-3866 to subjects with varying degrees of RI, where possible, to those of healthy matched control subjects.
 
Estimation 2: The Ae0-24, Fe, and CLr following a single IV dose of MK-3866 administered to subjects with varying degrees of RI will be estimated and compared to those estimated in mean healthy matched control subjects.
 
Objective 3: To evaluate the safety and tolerability of the administration of a single IV dose of MK-3866 in subjects with varying degrees of RI.
 
Exploratory Objective:
 
Objective: To explore the relationship between eGFR and pharmacokinetics (e.g. CLr and AUC0-∞) of MK-3866 using a model-based approach.

--	---

	Planned Exploratory Biomarker:  Objective: To explore the relationship between genetic variation and response to the treatment(s) administered, and mechanisms of disease. Variation across the human genome may be analyzed for association with clinical data collected in this study.																																			
Summary of Study Design:	
This is an open-label, 2-part, single dose study in renal impaired and healthy control subjects. Parts 1 and 2 of the study may be conducted concurrently.
 
Study parts and assignment to a renal function group will be as follows:
 
  
 Panel	Renal Function	N	eGFR (mL/min/1.73m^2)*	
   
 Part 1	
 
 A	Mild	8	<math>60 \leq \text{eGFR} < 90</math>	
 
 B	Moderate	8	<math>30 \leq \text{eGFR} < 60</math>**	
 
 C	Severe	8	< 30 not on dialysis	
 
 D	Healthy Matched Control	<math>\geq 8</math> (up to 24)	<math>\geq 90</math>	
 
 Part 2	
 
 E	ESRD requiring HD	8	requiring HD	
  
 
* Estimated glomerular filtration rate (eGFR) based on Modification of Diet in Renal Disease (MDRD) equation at screening. Baseline eGFR will be obtained by taking the mean of the eGFR obtained from screening and from historical values within a 3-month period from screening. If no historical measurement is available, a second baseline eGFR sample will be taken during the screening period (<math>\geq 72</math> hours apart) and the mean of the two values will be used for group assignment; the second baseline eGFR sample may be obtained at the time of check-in.
 
** Reasonable efforts will be made to enroll at least 2 subjects with eGFR values of 30 - 40 mL/min/1.73m^2
				Panel	Renal Function	N	eGFR (mL/min/1.73m  )*	Part 1				A	Mild	8	$60 \leq \text{eGFR} < 90$	B	Moderate	8	$30 \leq \text{eGFR} < 60$ **	C	Severe	8	< 30 not on dialysis	D	Healthy Matched Control	$\geq 8$ (up to 24)	$\geq 90$	Part 2				E	ESRD requiring HD	8	requiring HD
Panel	Renal Function	N	eGFR (mL/min/1.73m  )*																																	
Part 1																																				
A	Mild	8	$60 \leq \text{eGFR} < 90$																																	
B	Moderate	8	$30 \leq \text{eGFR} < 60$ **																																	
C	Severe	8	< 30 not on dialysis																																	
D	Healthy Matched Control	$\geq 8$ (up to 24)	$\geq 90$																																	
Part 2																																				
E	ESRD requiring HD	8	requiring HD																																	

	
Part 1:
 
Subjects in Panels A, B, C, and D will receive a single IV dose of MK-3866. Plasma samples will be taken at pre-specified time points up to 72 hours postdose, depending on the panel and urine samples will be collected at pre-specified time points up to 24 hours postdose, where possible, for pharmacokinetic assessment of MK-3866.
 
Part 2:
 
Subjects in Panel E will receive a single IV dose of MK-3866 on two separate occasions.
 
In Period 1, subjects will receive a single IV dose of MK-3866 immediately following their normally-scheduled HD, followed by 72 hours plasma sampling and by 24 hours urine collection, where possible, for pharmacokinetic assessment of MK-3866.
 
In Period 2, subjects will receive a single IV dose of MK-3866 approximately 30 minutes prior to their normally scheduled HD followed by 72 hours plasma sampling and by 24 hours urine collection, where possible, for pharmacokinetic assessment of MK-3866. During this dialysis session, additional plasma and dialysate samples will be taken for MK-3866 analysis.
 
There will be a washout period of at least 7 days between MK-3866 dosing in Periods 1 and 2 of Part 2.
 
Both Parts:
 
All subjects who received at least one dose of MK-3866 will return to the Clinical Research Unit (CRU) approximately 14 days after the last dose for follow-up procedures, and to determine if any adverse events have occurred since the last study visit.

Blinding:	This is an open-label study.
Number of Subjects:	
Subjects with RI:
 
Up to thirty-two (32), adult, male and female (non-childbearing potential only) subjects will be enrolled.
 
Panel A: Eight (8) subjects with mild RI.
 
Panel B: Eight (8) subjects with moderate RI.
 
Panel C: Eight (8) subjects with severe RI.
 
Panel E: Eight (8) subjects with ESRD requiring HD.

	
Subjects with mild (Panel A), moderate (Panel B), and severe (Panel C) RI and those with ESRD (Panel E) shall be enrolled in parallel, and each panel shall enroll a minimum of 2 subjects of each gender.
 
Healthy Matched Control Subjects:
 
Panel D: At least 8 (up to 24) healthy subjects (eGFR <math>\geq</math> 90 mL/min/1.73 m^2), matched to the mean age (<math>\pm</math> 15 years), gender, and mean body mass index (BMI; <math>\pm</math> 10%) of subjects in the mild, moderate, severe RI, and subjects with ESRD panels (Panels A, B, C, and E).
 
Enrolment of 8 healthy matched control subjects (Panel D) will commence following the completion of enrolment of Panels A and B. Each healthy control subject will be matched to the mean age (<math>\pm</math> 15 years) and the mean BMI (<math>\pm</math> 10%) of the subjects in Panels A and B combined. There should be a minimum of 2 subjects of each gender in each panel.
 
The data from the already enrolled healthy subjects who satisfy the gender, mean age and BMI matching criteria of the RI subjects in each of Panels C and E will be used. However, if any of the healthy subjects do not meet the matching criteria described above, additional healthy subjects will be enrolled to result in a total of 8 healthy subjects who match the mean age (<math>\pm</math> 15 years) and the mean BMI (<math>\pm</math> 10%) of each of Panels C and E. The gender of the additional healthy subject(s) will be selected to ensure that there is a minimum of 2 subjects of each gender in the group of subjects within Panel D who match with each of the Panels C and E.
 
The pharmacokinetic comparisons between each renally impaired panel (Panels A, B, C, and E) and healthy controls (Panel D) will include only the control subjects who meet the matching criteria for the respective RI panel.

Dosage, Dosage Form, Route, and Dose Regimen:	
Part 1:
 
Subjects will receive a single IV infusion of 200 mg MK-3866 at Hour 0 on Day 1.
 
Part 2:
 
Subjects will receive a single IV infusion of 200 mg MK-3866 at Hour 0 on Day 1, immediately after completion of the scheduled HD (Period 1), and at Hour 0 on Day 1, approximately 30 minutes prior to initiation of the scheduled HD (Period 2).

	
Both Parts:
 
Each IV infusion will be administered over 30 minutes (<math>\pm 5</math> minutes).
 
Hour 0 will be determined as the start of the infusion.

Key Assessments:	
Pharmacokinetics:
 
The following pharmacokinetic parameters will be calculated for MK-3866 in plasma, as appropriate, in all panels: AUC0-∞, AUC0-last, AUC0-24, Ce01 (Cmax), Tmax, elimination terminal t1/2, CL, and Vz.
 
The following pharmacokinetic parameters will be calculated for MK-3866 in urine, as appropriate, in all panels: Ae0-24, Fe, and CLR.
 
For subjects with ESRD on HD (Panel E only), the following pharmacokinetic parameters will also be calculated for MK-3866 in plasma, as appropriate: Ca, Cv, AUCD, AUC(1-4.5)Ca, and AUC(1-4.5)Cv, CLD, plasma and in dialysate: CD, AD, rr, AD, total, and CLD, dialysate.
 
Safety:
 
Safety will be monitored through physical examination, vital signs, 12-lead electrocardiograms (ECGs), adverse events and clinical laboratory tests. Summary statistics for the laboratory safety tests, 12-lead ECGs, and/or vital signs may also be computed and provided, as deemed clinically appropriate.

## 6 STUDY EVENTS FLOW CHART

### 6.1 Subjects with Mild (Panel A), Moderate (Panel B), and Severe (Panel C) RI and Healthy Subjects (Panel D) – Part 1

Study Procedures a	S b	Study Days																		FU c		
		-2 /-1		1														2		3		
	Days →	Hours →	(C-I) d	P	0	0.5	0.75	1	1.5	2	3	4.5	6	8	10	12	24	36	48	60	72	
Administrative Procedures																						
Informed Consent	X																					
Informed Consent for Future Biomedical Research	X																					
Inclusion/Exclusion Criteria	X	X																				
Medical History	X																					
Safety Evaluations																						
Full Physical Examination e	X	X																X f		X f		X f X
Height	X																					
Weight	X	X																				X
Assessment of Renal Function g	X																					
12-Lead Electrocardiogram h	X		X i		X					X								X f		X f		X f
Vital Signs (heart rate & blood pressure)	X		X i		X				X			X				X		X f		X f		X f X
Vital Signs (respiratory rate & temperature)	X																					
Hematology, Ser Chemistry j , and UA	X	X																	X			X
Serum Pregnancy Test (female subjects only)	X	X																				
Serum FSH (postmenopausal females only)	X																					
Urine or Saliva Drug and Cotinine Screen	X	X																				
Urine or Breath Alcohol Screen	X	X																				
HIV/Hepatitis Screen	X																					
Adverse Events Monitoring	X-----																					X
Prior and Concomitant Medication Monitoring	X-----																					X

Study Procedures a	S b	Study Days																		FU c	
		-2 /-1		1														2		3	
	Days →	Hours →	(C-I) d	P	0	0.5	0.75	1	1.5	2	3	4.5	6	8	10	12	24	36	48	60	72
Study Drug Administration / Pharmacokinetics																					
MK-3866 IV Administration					X----X																
Blood for MK-3866 Pharmacokinetics k				X		X l	X	X	X	X	X	X	X	X	X	X	X	X	X	X	
Urine for MK-3866 Pharmacokinetics m				X	X																
Other Procedures																					
Blood for Genetic Analysis n				X																	
Confinement in the CRU for Healthy				X-																	
Confinement in the CRU for mild and moderate RI				X-																	
Confinement in the CRU for severe RI				X-																	
Visit and Post-Trial Visit	X																				X

a. For details on Procedures, refer to [Section 10](#) and/or corresponding appendices.

b. Within 28 days prior to dosing.

c. All subjects who received at least one dose of MK-3866 will return to the Clinical Research Unit (CRU) approximately 14 days after the last dose for follow-up procedures, and to determine if any adverse events have occurred since the last study visit.

d. Check-in: Subjects will be admitted to the CRU on Day -2 or Day -1, at the time indicated by the CRU.

e. Symptom-driven physical examinations may be performed at other times, at the Investigator's or designee discretion.

f. To be performed only once as the last study procedure for each panel: at 24 hours post start of infusion for healthy controls (Panel D); 48 hours for subjects with mild and moderate RI (Panel A and B), and 72 hours for subjects with severe RI (Panel C), or prior to early termination from the study.

g. Baseline eGFR will be obtained by taking the mean of the eGFR obtained from screening and from historical values within a 3 months period from screening. If no historical measurement is available, a second baseline eGFR sample will be taken during the screening period ( $\geq 72$  hours apart) and the mean of the two values will be used for group assignment; the second baseline eGFR sample may be obtained at the time of check-in.

h. Triplicate 12-lead ECGs to be performed at screening and for predose ECG measurement. Single 12-lead ECGs to be performed for all postdose ECG measurements.

i. To be performed within 24 hours prior to dosing.

j. Samples for serum chemistry will be obtained following a fast of at least 8 hours; however, in case of discontinuations or rechecks, subjects may not have fasted for 8 hours prior the serum chemistry sample is taken. For subjects who are anuric, urine samples for urinalysis will not be collected.

- k. The plasma pharmacokinetic sampling time points will be completed at 24 hours post start of infusion for healthy controls (Panel D); 48 hours for subjects with mild and moderate RI (Panel A and B), and 72 hours for subjects with severe RI (Panel C).
- l. The 0.5 hour blood sample for MK-3866 pharmacokinetic should be collected at the end of the infusion.
- m. Urine collection intervals are: pre-dose (spot collection), 0 - 4, 4 - 8, 8 – 12, and 12 - 24 hours postdose. For subjects with RI, urine samples will be collected whenever possible, as subjects may not be able to produce urine at each interval. For subjects who are anuric, urine samples will not be collected.
- n. This sample should be drawn for planned analysis of the association between genetic variants in DNA and drug response. This sample will not be collected at the site if there is either a local law or regulation prohibiting collection, or if the IRB/IEC does not approve the collection of the sample for these purposes. If the sample is collected, leftover extracted DNA will be stored for future biomedical research if the subject signs the FBR consent. If the planned genetic analysis is not approved, but FBR is approved and consent is given, this sample will be collected for the purpose of FBR.

Abbreviations: C-I = Check-in, CRU = Clinical Research Unit, FU = Follow-Up, FSH = Follicle Stimulating Hormone, HIV = Human Immunodeficiency Virus, IV = Intravenous, P = Predose, RI = Renal Impairment, S = Screening, Ser = Serum, UA = Urinalysis

## 6.2 Subjects with ESRD on Dialysis (Panel E, Period 1 + Period 2) – Part 2

Study Procedures a	S b	Study Days in Period 1 (MK-3866 Administered Post-Dialysis) c																		
	Days → Hours →	-2 /-1	1												2					
		(C-I) d	P	0	0.5	0.75	1	1.5	2	3	4	4.5	6	8	10	12	24	36	48	60
Administrative Procedures																				
Informed Consent		X																		
Informed Consent for Future Biomedical Research		X																		
Inclusion/Exclusion Criteria	X	X																		
Medical History	X																			
Safety Evaluations																				
Full Physical Examination e	X	X																		X f
Height	X																			
Weight	X	X																		
12-Lead Electrocardiogram g	X		X h		X				X									X		X f
Vital Signs (heart rate & blood pressure)	X		X h		X				X				X				X			X f
Vital Signs (respiratory rate & temperature)	X																			
Hematology, Serum Chemistry i , and UA	X	X																X		X f
Serum Pregnancy Test (female subjects only)	X	X																		
Serum FSH (postmenopausal females only)	X																			
Urine or Saliva Drug and Cotinine Screen	X	X																		
Urine or Breath Alcohol Screen	X	X																		
HIV/Hepatitis Screen	X																			
Adverse Events Monitoring	X																	X		
Prior and ConMed Monitoring	X																	X		
Study Drug Administration/ Pharmacokinetics																				
MK-3866 IV Administration						X-----X j														
Blood for MK-3866 Pharmacokinetics			X k		X l	X	X	X	X	X	X	X	X	X	X	X	X	X	X	X m
Urine for MK-3866 Pharmacokinetics n					X													X		
Other Procedures																				
Blood for Genetic Analysis o				X																
Confinement in the CRU		X																	X	
Visit	X																			

Study Procedures a	Days → Hours →	Study Days in Period 2 (MK-3866 Administered Pre-Dialysis) c																		FU p		
		-2 / -1		1																		
		(C-1) d	P	0	0.5	0.75	1	1.5	2	2.5	3	3.5	4	4.5	6	8	10	12	24	36	48	60
Safety Evaluations																						
Full Physical Examination e		X																		X f	X	
Weight		X																				X
12-Lead Electrocardiogram g			X h																			
Vital Signs (heart rate & blood pressure)		X h		X			X								X				X i	X		
Vital Signs (respiratory rate & temperature)		X																				
Hematology, Serum Chemistry i , and UA		X																	X		X i	X
Serum Pregnancy Test (female subjects only)		X																				
Urine/Saliva/Blood Drug Screen		X																				
Urine or Breath Alcohol Screen		X																				
Adverse Events Monitoring		X																				X
Prior and ConMed Monitoring		X																				X
Study Drug Administration / Pharmacokinetics																						
MK-3866 IV Administration				X----X																		
Blood for MK-3866 Pharmacokinetics		X		X l	X q	X	X	X	X	X	X	X m										
Dialysate for MK-3866 Pharmacokinetics r			X	X	X	X	X	X	X	X	X	X	X	X	X							
Urine for MK-3866 Pharmacokinetics n				X																		
Other Procedures																						
Hemodialysis s					X																	
Confinement in the CRU		X																				X
Post-Trial Visit																						X

- a. For details on Procedures, refer to [Section 10](#) and/or corresponding appendices.
- b. Screening: Within 28 days prior to the first dose.
- c. There will be a period of at least 7 days between MK-3866 dosing in Period 1 and Period 2.
- d. Check-in: Subjects will be admitted to the CRU on Day -2 or Day -1, at the time indicated by the CRU.
- e. Symptom-driven physical examinations may be performed at other times, at the Investigator's discretion.
- f. To be performed on Day 4 or prior to early termination from the study.
- g. Triplicate 12-lead ECGs to be performed at screening and for predose ECG measurements. Single 12-lead ECGs to be performed all postdose ECG measurements.

- h. To be performed within 24 hours prior to dosing.
- i. Samples for serum chemistry will be obtained following a fast of at least 8 hours; however, in case of discontinuations or rechecks, subjects may not have fasted for 8 hours prior the serum chemistry sample is taken. For subjects who are anuric, urine samples for urinalysis will not be collected.
- j. IV infusion will start immediately following the end of the scheduled HD in Period 1.
- k. The predose sample should be collected after HD and prior to the start of the infusion.
- l. The 0.5 hour blood sample for MK-3866 should be collected at the end of the infusion.
- m. If the next scheduled HD must be initiated prior the 72 hours postdose, a sample for MK-3866 analysis will be collected prior to HD.
- n. Urine collection intervals are: pre-dose (spot collection), 0 - 4, 4 - 8, 8 – 12, and 12 - 24 hours postdose. Urine samples will be collected whenever possible, as subjects may not be able to produce urine at each interval. For subjects who are anuric, urine samples will not be collected.
- o. This sample should be drawn for planned analysis of the association between genetic variants in DNA and drug response. This sample will not be collected at the site if there is either a local law or regulation prohibiting collection, or if the IRB/IEC does not approve the collection of the sample for these purposes. If the sample is collected, leftover extracted DNA will be stored for future biomedical research if the subject signs the FBR consent. If the planned genetic analysis is not approved, but FBR is approved and consent is given, this sample will be collected for the purpose of FBR.
- p. All subjects who received at least one dose of MK-3866 will return to the Clinical Research Unit (CRU) approximately 14 days after the last dose for follow-up procedures, and to determine if any adverse events have occurred since the last study visit.
- q. During HD, blood samples for MK-3866 will be collected from both the pre-dialyzer and post-dialyzer blood lines; thus 2 plasma samples per time point during HD will be taken. A blood sample (a pre-dialyzer and post-dialyzer) will also be obtained immediately before the HD is stopped, if this time point does not coincide with a time point that is already scheduled.
- r. Dialysate samples for determination of MK-3866 will be obtained pre-dialysis, post-dialysis (before the HD is stopped), and for 1 minute every half hour during HD.
- s. HD session will be initiated immediately following the 0.5-hour postdose blood draw.

Abbreviations: ConMed = Concomitant Medication, CRU = Clinical Research Unit, FU = Follow-Up, FSH = Follicle Stimulating Hormone, HIV = Human Immunodeficiency Virus, IV = Intravenous, HD = Hemodialysis P = Predose, RI = Renal Impairment, S = Screening, UA = Urinalysis

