#### **10.1.5 Hemodialysis (ESRD Subjects Only)**

ESRD subjects on HD will receive HD as per their regular schedule and blood and dialysate sampling be collected as outlined in the Study Events Flow Chart ([Section 6](#)).

Dosing in Period 1 will occur immediately following completion of a normally scheduled HD session. For subjects following a Monday, Wednesday, Friday HD schedule, MK-3866 will be administered immediately following their Friday HD session. For subjects following a Tuesday, Thursday, Saturday HD schedule, MK-3866 will be administered immediately following their Saturday HD session. The 72-hour HD (either Monday or Tuesday) should initiate immediately following the 72-hour blood draw. If HD must be initiated prior to 72 hours postdose, a sample for MK-3866 analysis will be collected prior to HD, and the time recorded.

Dosing in Period 2 will occur approximately 30 minutes prior to the normally scheduled HD session. For subjects following a Monday, Wednesday, Friday HD schedule, MK-3866 will be administered prior to their Friday HD session. For subjects following a Tuesday, Thursday, Saturday HD schedule, MK-3866 will be administered prior to their Saturday HD

session. The subsequent HD session should initiate immediately following the 30 minute blood draw.

In Period 2, the HD period will be approximately 4 hours for all subjects. Blood samples collected during HD will be collected from both the pre-dialyzer and post-dialyzer blood lines.

The blood flow, dialysate flow, and the make and model of the dialyzer will be recorded.

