### 11.1.3 Hemodialysis: Plasma and Dialysate

For subjects in Panel E, the following pharmacokinetic parameters for plasma MK-3866 will be calculated as appropriate:

Ca: Concentration in plasma entering the dialyzer line (arterial or pre-dialyzer line)

Cv: Concentration in plasma exiting the dialyzer (venous or post-dialyzer line)

AUCD: Plasma AUC values determined from Ca versus time profile during the dialysis period (0.5-4.5 hours) using 'linear up, log down' calculation method option in WinNonlin

AUC(1-4.5)Ca: Plasma AUC values determined from Ca versus time profile during the dialysis period from 1 hour to 4.5 hours using 'linear up, log down' calculation method option in WinNonlin

AUC(1-4.5)Cv: Plasma AUC values determined from Cv versus time profile during the dialysis period from 1 hour to 4.5 hours using 'linear up, log down' calculation method option in WinNonlin

CLD,plasma: Dialysis clearance based on plasma, calculated as  $Q \times R \times (AUC[1-4.5]Ca - AUC[1-4.5]Cv) / AUC(1-4.5)Ca$ , where Q is the flow rate of blood through the dialyzer, and R is the ratio of blood drug concentration to plasma drug concentration

For subjects in Panel E, the following pharmacokinetic parameters for dialysate MK-3866 will be calculated as appropriate:

CD:	Concentration in dialysate samples
AD:	Amount of drug recovered from each dialysate collection, calculated as: CD x dialysate volume
rr:	Rate of drug removal, calculated as: (CD x dialysate flow rate)
AD,total:	Cumulative amount of drug recovered from the dialysate will be obtained by integrating the rr versus time profile over the dialysis session duration, using actual times relative to the start time of dialysis
CLD,dialysate:	HD clearance based on dialysate, calculated as: AD,total/AUCD

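### Section 11.1.3 does not say how the dialysate removal rate is obtained for the opening half hour of dialysis; if the pre-dialysis sample serves as time 0, AD,total and CLD,dialysate come out low

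*Combined protocol and SAP*

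**What the plan says.** Timing of dialysis (flow chart 6.2, Period 2 footnotes, and section 10.1.5):

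- On the early blood sample: "The 0.5 hour blood sample for MK-3866 should be collected at the end of the infusion".
- On the start of dialysis: "HD session will be initiated immediately following the 0.5-hour postdose blood draw".
- On its length: "In Period 2, the HD period will be approximately 4 hours for all subjects". A session with perfect timing therefore runs from 0.5 h to 4.5 h after the start of infusion.

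Dialysate samples (footnote r to flow chart 6.2) "will be obtained pre-dialysis, post-dialysis (before the HD is stopped), and for 1 minute every half hour during HD". Section 10.2.3 refers back to the flow chart for the sampling times.

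Parameters (section 11.1.3):

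- The definition of rr reads "Rate of drug removal, calculated as: (CD x dialysate flow rate").
- The method for AD,total is "integrating the rr versus time profile over the dialysis session duration, using actual times relative to the start time of dialysis", so the whole session counts from its first minute.
- The dialysate-based clearance then takes that amount as its numerator: "HD clearance based on dialysate, calculated as: AD,total/AUCD".
- AUCD is the Ca area over 0.5-4.5 h.
- CLD,plasma uses a later window for both of its areas. The Ca area is described as "Plasma AUC values determined from Ca versus time profile during the dialysis period from 1 hour to 4.5 hours", and the Cv area has the same limits.

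The linear-up/log-down rule is named for the plasma areas only. No integration rule is given for rr, no value or method for rr at the start of dialysis, and no statement of what the pre-dialysis dialysate sample is for.

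**The concern.** Dialysis begins at about the peak plasma concentration, so the removal rate should be highest in the first minutes and fall from there. On the plain reading of footnote r, no dialysate is collected during that first half hour. The fluid sampled before dialysis has not met the subject's blood, and the previous dose was at least 7 days earlier. Its concentration should be zero, and so should the rr calculated from it.

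Two straightforward ways of integrating the scheduled samples both lose drug. Joining a zero at time 0 to the 30-minute value replaces the highest part of the curve with a triangle. Starting at the 30-minute sample omits that part altogether. The denominator AUCD counts the same half hour in full from Ca, so the numerator and denominator of CLD,dialysate no longer cover the same exposure. CLD,plasma avoids this because both of its areas start at 1 h.

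AD,total and CLD,dialysate are among the dialysate parameters named under secondary Objective 1, the extent of removal by HD, and section 7.2.1 says the study should inform dosing around dialysis. An error in the same direction in every subject does not average out over eight subjects. It would also put CLD,dialysate below CLD,plasma through arithmetic alone, which a reader could take for a real difference.

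**Working it through.** **Check of the schedule against the plan's own count.** The documents give no figure for AD,total or CLD,dialysate. The figure that tests the HD sampling schedule is the 47 blood time points in Table 3. Reading the flow chart columns through 72 h, Period 1 has 18 samples and Period 2 has 20. Adding one post-dialyzer sample at each HD time from 0.75 h to 4.5 h (0.75, 1, 1.5, 2, 2.5, 3, 3.5, 4, 4.5: nine times) gives 18 + 20 + 9 = 47. With pairs only from 1 h the total is 46. So 47 fits paired plasma sampling 15 minutes into HD; footnote r names no matching dialysate sample.

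**Model (assumption).** During a perfectly timed 4 h session, rr(t) = rr0·exp(−kt), with t in hours from the start of HD and rr0 = 1.

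- True AD,total = (1 − exp(−4k))/k.
- True first half hour = (1 − exp(−0.5k))/k.
- Zero at time 0, first sample at 30 min: the first half hour becomes a triangle, 0.25·exp(−0.5k).
- Interval dropped: the first half hour contributes nothing.
- Log-down integration is exact for the rest of this curve, so the whole error lies in the opening interval. AUCD, which has a Ca value at 0.5 h, is unbiased in the same model, so CLD,dialysate carries the same percentage error as AD,total.

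**Worked line, k = 0.3 per h.** True total = (1 − exp(−1.2))/0.3 = 2.329. True first half hour = (1 − 0.8607)/0.3 = 0.464. Triangle = 0.25 × 0.8607 = 0.215. Shortfall = (0.464 − 0.215)/2.329 = 10.7%. If the interval is dropped: 0.464/2.329 = 19.9%.

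**Range of k.** The documents give no decline rate on dialysis. Section 7.2.2 projects AUC 202 µM·hr and Ceoi 24 µM in ESRD, so a crude k off dialysis is 24/202 = 0.12 per h, and dialysis can only raise it. The assumed range is 0.1 to 0.7 per h.

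| Handling of the opening interval | k = 0.1 | 0.3 | 0.5 | 0.7 |
|---|---|---|---|---|
| Zero at time 0, first sample at 30 min | −7.6% | −10.7% | −14.3% | −18.3% |
| Same, plain linear trapezoid throughout | −7.6% | −10.5% | −13.9% | −17.6% |
| Zero at time 0, plus a dialysate sample at 0.75 h (15 min into HD) | −3.8% | −5.4% | −7.2% | −9.3% |
| Interval dropped | −14.8% | −19.9% | −25.6% | −31.4% |
| Zero at time 0, plus a sample in the first minute of HD | −0.3% | −0.4% | −0.5% | −0.6% |
| rr back-extrapolated to the start of HD (log-down) | 0% | 0% | 0% | 0% |

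**Narrower range tied to the projection.** For one compartment and a 0.5 h infusion, Ceoi/AUC = (1 − exp(−0.5·koff))/0.5. Setting this to 24/202 gives koff = −2·ln(1 − 0.0594) = 0.1225 per h. If dialysis clearance is 1, 2 or 3 times the patient's own clearance (assumed), k = 0.245, 0.3675 or 0.49 per h. The zero-start shortfall is then 9.8%, 11.9% or 14.1%; with a 0.75 h dialysate sample it is 4.9%, 6.0% or 7.1%; with the interval dropped it is 18.5%, 21.8% or 25.3%.

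**The case against.** The strongest objection is that the plan prescribes none of the biased calculations. It does not say that the pre-dialysis sample enters the integral, and it leaves the method for rr at time 0 open. An analyst who back-extrapolates rr to the start of HD gets the right answer. This stands. A reader might infer that AD,total and CLD,dialysate will be understated in every subject; the documents do not support that, because the bias depends on a choice they leave unstated.

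Second, a reader might infer that the plan has no dialysate sample at all early in HD. That cannot be shown either. Section 10.2.3 makes the flow chart govern, and its Period 2 dialysate row came through as an unbroken run of about 13 marks, where footnote r needs only nine (pre-dialysis plus eight half-hourly samples). The neighboring blood row is visibly collapsed, so column positions prove nothing, and a 0.75 h dialysate mark can be neither confirmed nor excluded. Half-hourly collection could also be read to include the first minute. These points change the size of the error. They do not supply the missing rule.

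Third, the drug-free pre-dialysis sample is an inference, though a sound one, and the decline rate and one-compartment shape are assumptions. The 15-31% figures also require leaving out an interval that section 11.1.3 says the integral should cover.

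Fourth, the consequences are limited. Section 11.2.3.3 gives the dialysate parameters listings and descriptive statistics only. The modeled HD/non-HD ratios use no dialysate data, and CLD,plasma is untouched. This stands and lowers the severity.

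**Conclusion.** The concern holds in conditional form. On the plain reading of footnote r, the numerator of CLD,dialysate has no in-session measurement for a half hour that its denominator counts in full, and section 11.1.3 does not say how that half hour is to be filled. Using the pre-dialysis zero makes AD,total and CLD,dialysate low by roughly 8-18% for k of 0.1-0.7 per h, or 10-14% if dialysis clearance is 1-3 times the patient's own. This happens even when the session runs exactly from 0.5 h to 4.5 h, and choosing between the linear and log-down rules does not remove it. The error could be half as large or near zero, depending on the flow chart marks and the analyst's method.

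Severity is low to moderate: these are descriptive secondary parameters. It is still more than a missing detail, because simply integrating the scheduled samples gives a low answer and a better calculation is available from data already planned.

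**What to change.** In section 11.1.3:

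1. State that the pre-dialysis dialysate sample is an assay blank and is not used as rr at time 0. Name the integration rule for rr.
2. Define CLD,dialysate as the integral of rr from the first to the last in-session dialysate sample, divided by the Ca AUC over that same interval. If the first sample is at 1 h and the session ends at 4.5 h, this is the 1-4.5 h Ca AUC already planned.
3. Obtain AD,total as that integral plus, for the opening interval, the same clearance times the Ca AUC from the start of dialysis to the first dialysate sample.
4. Say in the report that the opening part of AD,total is calculated from plasma, assuming constant dialysis clearance.

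In flow chart 6.2, make footnote r state the time of the first in-session dialysate sample, so that the interval in steps 2 and 3 is unambiguous.

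The cost is analysis wording only, with no new samples. The downside is that one interval of AD,total is calculated rather than measured in dialysate. In the model above, where dialysis clearance is constant, this calculation recovers both parameters without bias.
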